Pharmacogenomics of Thiazolidinediones

NCT01135394

2006-11-27

RESEARCH PLAN

A. SPECIFIC AIMS

The Thiazolidinediones (TZDs) are a class of insulin sensitizing drugs used in the treatment of type 2 diabetes (T2DM). In addition, trials suggest that the TZDs may be useful in the prevention of progression from impaired glucose tolerance to T2DM and have salutary effects on other aspects of the metabolic syndrome. However, clinical and mechanistic studies indicate that not all patients exhibit the expected response to TZDs. Approximately 1/3 of those treated show little or no improvement in insulin sensitivity or HbA1c.

The TZDs are ligands for the nuclear receptor peroxisome proliferator activated receptor-gamma (PPAR γ). When this receptor is activated by TZDs, many genes involved in adipogenesis and insulin signaling are up- or down-regulated.

The overall objective of this proposal is to define the molecular and genetic basis of TZD responsiveness using a phenotype to genotype approach and state-of-the-art functional genomics and high-throughput genetics. Our ***hypotheses*** are:

- (1) Differences in clinical response (primarily improvement in insulin sensitivity) can be defined at the molecular level as differences in expression of genes involved in TZD-activated pathways.
- (2) Genes whose expression change is correlated to clinical response can be identified through cDNA microarrays of muscle and fat, the two target tissues for TZDs.
- (3) Sequence variants in these candidate genes will determine TZD response, particularly sequence variants within regulatory regions.

To directly test these hypotheses, the ***Specific Aims*** of this proposal are to:

1. Perform comprehensive testing in 75 individuals before and after a 3-month rosiglitazone intervention and characterize the variability in TZD response at the physiological, cellular, and molecular levels. The primary TZD response trait will be changes in insulin sensitivity as measured by an intravenous glucose tolerance test (IVGTT). We will also define secondary response traits, which will include body fat composition and distribution (DXA and abdominal CT), serum lipid levels (HDL, LDL, triglycerides, lipoprotein particle sizes), inflammatory markers (hsCRP, SAA, IL1 β , IL6, TNF α), prothrombotic factors (plasminogen activator inhibitor 1; PAI-1), adipokines (leptin, adiponectin), and adipocyte metabolism (glucose uptake, lipolysis). From these data, we will:

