[figure not shown]

Figure 7. Haplotype structure of omentins 1 and 2 as imaged by Haplovview.

D. RESEARCH DESIGN AND METHODS

1. Study Overview and Rationale

The overall objective of this proposal is to define the molecular and genetic basis of the inter-individual variation in response to TZDs. We will test the hypothesis that inter-individual variability in TZD response is due, in part, to genetic influences, more specifically sequence variants in one or more candidate genes. The general approach we will use is a phenotype to genotype approach. We will not only be looking at phenotypes on the whole-body level, but also obtain muscle and fat tissue samples to study more immediate phenotypes all the way down to the gene expression level. Because TZDs act by binding to the nuclear receptor PPAR γ to elicit direct and indirect changes in gene expression that ultimately exert their phenotypic effects, we reason that a phenotype to molecular (gene expression) profile to genotype approach would have the highest likelihood of identifying the responsible genes and their variants.

[figure not shown]

Fig. 8. Schematic of overall study design

The proposed study will expand upon an ongoing study of the pharmacogenomics of PPAR γ in which sophisticated phenotyping and microarray studies of fat and muscle are already well underway (see Preliminary Studies). A schematic of the study design and timeline are shown in Figures 8 and 9. We will define the genes whose regulation correlates to TZD response. Comparisons of gene expression profiles of the same tissue in the same person pre- and post- intervention should minimize many of the problems associated with most microarray experimental designs and should minimize the number of false positive (and false negative) results.

Furthermore, we will confirm these differences by real-time PCR on RNA from the same sample in which the microarray studies were performed. Confirmed genes whose up- or down-regulation is

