Specific Aim 1c. We will perform cDNA microarray analysis of muscle and fat before and after 3 months of rosiglitazone therapy for the purpose of identifying genes (and their corresponding pathways) whose changes in expression correlate with the change in insulin sensitivity in response to TZDs. This proposed experiment extends our ongoing work from the Pharmacogenetics of PPAR γ Study (see Preliminary Data).

We will initially compute the change in expression levels for each of the 40,000 examined genes. We will then use correlation analysis to determine the genes whose changes in expression levels best correlate with change in insulin sensitivity and the other clinical outcomes. We anticipate that some genes will be up-regulated in response to TZD therapy and others will be down-regulated, and the magnitude of these changes will correlate with clinical response. Our goal will be to identify the 100 genes whose differential in up (or down) regulation most closely correlate with clinical response.

We recognize that the results of microarray experiments must be interpreted cautiously, especially in light of the multiple comparisons issue. However, the major goal of our experiment is to identify genes that might mediate the response to TZDs and which hence might be candidates for further studies. Our selection of genes will therefore be guided by several factors, including the strength of the statistical evidence, and our best understanding of the likely function of the differentially expressed genes. Please see the Microarrays section below for a description of the statistical analysis of the microarray data.

f. Laboratory methods:

Serum/plasma assays. Cytokines will be measured by the Cytokine Core Laboratory at the University of Maryland by ELISA (see Letter from [name]). C-peptide, leptin and adiponectin will also be measured by ELISA at the GCRC Biochemistry Core Laboratory. Lipid profile will be measured by Quest and lipoprotein particle sizes will be measured by NMR (Liposciences, Raleigh, NC).

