Statistical approach. To study the gene expression profiles that are related to the 3-month rosiglitazone intervention, we will compare the expression profile of the muscle (and fat) tissues from pretreatment subjects to that from post-treatment subjects. We will calculate and normalize gene expression levels by the Robust Multichip Average method (RMA) (37) and quantile normalization (11). The statistical significance of these comparisons will be assessed using LIMMA package software (27) (a linear model approach implemented in Bioconductor) or non-parametric methods (e.g., Kruskal-Wallis- or Mann-Whitney U-tests), using SAS software. A critical issue in microarray analysis is to avoid a high "false discovery rate" (9) (FDR; the probability that a gene is incorrectly identified as differentially expressed), due to the large number of genes compared. We will consider genes to be differentially expressed only if they meet criterion values for fold-change and p-value (for example, >1.5 and <0.05, respectively). For each analysis of differential expression, we will experiment with different combinations of criterion values and calculate the resultant FDR (using MULTTEST package in Bioconductor (61)) for each set of criteria, until we obtain acceptable stringency for fold-change, statistical significance and FDR (we anticipate using conservative FDRs in the range of 1-5%).

To study the association between these differentially expressed (DE) genes and the response of the primary and secondary traits to TZDs, for each DE gene, we will generate linear regression models using the change in the response of the primary (i.e., insulin sensitivity) and secondary responses to TZDs as dependent variables and the gene expression change in response of the treatment and demographic and clinical measures as the independent variables. For the regression models, we will report the adjusted squared correlation coefficient (R^2_{adj}), which corrects for the degrees of freedom. The association between each DE gene and each trait in response to TZDs can be measured by the adjusted squared correlation coefficient. The overall association with primary and secondary traits can be based on the score that is calculated as the weighted sum of the corresponding the adjusted squared correlation coefficients. The weights can be determined by principal component analysis. The importance of each gene can be determined by its score.

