We will then analyze the biological significance of the genes which are identified by the above analyses, using GenMAPP (15) (Gene MicroArray Pathway Profiler) and MAPPFinder (19). GenMAPP facilitates the viewing and analysis of gene expression data in the context of biological pathways. The pathways are represented in a special file format called a "MAPP". The MAPPs are independent of the gene expression data and can be used to group genes and view data by any organizing principle. MAPPFinder uses GenMAPP and the Gene Ontology (GO) database (<http://www.geneontology.org>) to identify biological trends in gene expression data. MAPPFinder can use the terminology and organizing principles of the GO database, or user-defined MAPPs. The three organizing principles of GO are "molecular function", "biological process" and "cellular component", which are attributes of gene products. Each of these terms has sub-terms ("children") organized in a tree-like structure. The terms are assigned independently, such that each gene can fall into all three groups. Our analysis will identify (on the basis of z-score and permuted p-value) molecular functions, biological processes or cellular components that are potentially influential in the subjects in regard to TZD treatment. Based on microarray and functional genomic analyses and Q-RT-PCR validation, we will select 100 candidate genes that influence TZD response for Aim 2 study.

Software. The statistical software packages SAS, Bioconduct and R (27) are the primary tools for most statistical analysis. SAS software, which is installed on our computers, is a combination of programs originally designed to perform statistical analysis of data. R is a free software environment for statistical computing and graphics. Bioconductor is an open source and open development software project for the analysis and comprehension of genomic data. These approaches as well as others that emerge during the course of this project in the continually evolving field of microarray analysis will be utilized to process the data obtained in our microarray experiments.

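### The 100 genes are picked by rank of association with response with no error control on that association, so the plan cannot find that no gene tracks response

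*Combined protocol and SAP*

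**What the plan says.** Section A (Specific Aims) sets the aims up as direct tests of three hypotheses. The second is that microarrays of muscle and fat can identify genes whose expression change is correlated with clinical response.

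The selection is described in two places.

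- **Section D.2.e, Specific Aim 1c:** "We will initially compute the change in expression levels for each of the 40,000 examined genes". These changes are correlated with the change in insulin sensitivity and the other outcomes, and then: "Our goal will be to identify the 100 genes whose differential in up (or down) regulation most closely correlate with clinical response". The section adds that judged gene function will also guide selection, urges caution over multiple comparisons, and refers to the Microarrays text for the statistical methods.
- **Section D.2.f, Microarrays, Statistical approach:** genes are first screened for pre/post change, using a fold-change and p-value gate. The FDR, expected to be 1-5%, belongs to this screen: "For each analysis of differential expression, we will experiment with different combinations of criterion values and calculate the resultant FDR". Response is then regressed on expression change for each gene that passes. Adjusted R-squared values are combined across traits into a weighted score, and "The importance of each gene can be determined by its score". After pathway analysis and PCR, "we will select 100 candidate genes that influence TZD response for Aim 2 study".

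On PCR, section D.1 says "we will confirm these differences by real-time PCR on RNA from the same sample in which the microarray studies were performed". The Quantitative Real-time PCR text in D.2.f also specifies the same RNA and gives more precise quantification as the reason. The heading statement of Aim 2 describes the resulting genes as ones whose regulation correlates with response.

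**The concern.** A gene can change on the drug in nearly everyone and still say nothing about who responds. Controlling the FDR for pre/post change therefore gives no protection when genes are ranked on their relation to response, and that second step only ranks. With the list length fixed in advance, the procedure has no outcome that counts against hypothesis 2.

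Later steps do not fill the gap. PCR reads the same RNA from the same people, so it can correct array measurement error but not a correlation that arose by chance in those 75 subjects. The DPP and TRIPOD analyses in Aim 3 use new subjects, but they test SNPs in the chosen genes and not the expression-response correlation.

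At stake is what can be said at the end of Aim 1c: that 100 genes correlate with or influence response, or only that 100 genes were chosen for genotyping.

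**Working it through.** **Inputs from the document.** n = 75 ("Perform comprehensive testing in 75 individuals before and after a 3-month rosiglitazone intervention", section A). 40,000 genes (D.2.e), in each of two tissues. List size 100. Pilot genes passing fold change 1.5 and p < 0.05: 167 in fat and 141 in muscle, together 308 (section C.4, Microarray studies).

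**Assumptions.** Independent genes; simple correlation with one response trait in place of the weighted score; two-sided 5% for nominal significance. The size of the gated pool is unknown, so three sizes are used: 40,000 (the literal D.2.e text, no gate), 2,000 (illustrative) and 308 (pilot count).

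**1. The plan's own correlation figure.** D.2.e gives 80% power for r = 0.31 with 75 subjects. The noncentrality is 0.31 × √75 / √(1 − 0.31²) = 2.82 and the critical t on 73 df is 1.993, giving power 79.6%. The figure reproduces, but it is for a single test in Aim 1b. No operating figure is given for the 100-gene rule.

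**2. The rule when no gene is related to response.** For m genes the 100th smallest p-value is about 100/m. With t the matching two-sided quantile on 73 df, r = t / √(t² + 73). The number nominally significant in the pool averages 0.05m, and at most 100 can be listed.

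| Pool m | 100/m | t | 100th abs(r) | Largest abs(r), simulated | Nominally significant among the 100 |
|---|---|---|---|---|---|
| 40,000 | 0.0025 | 3.13 | 0.34 | 0.48 | 100 (0.05m = 2,000) |
| 2,000 | 0.05 | 1.99 | 0.23 | 0.41 | about 96 |
| 308 | 0.325 | 0.99 | 0.12 | 0.35 | about 15 (0.05m = 15.4) |

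For m = 2,000 the count has mean 100 and SD √(2,000 × 0.05 × 0.95) = 9.75. Capped at 100, it averages about 100 − 0.399 × 9.75 = 96. For m = 40,000, blocks of genes correlated at 0.5 gave almost the same 100th |r| (0.343).

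**3. Does the pre/post gate help?** In one simulation, 2,000 genes changed on drug by 1 SD with no relation to response. All 2,000 passed the gate at FDR 1%, and the top 100 still had |r| from 0.23 to 0.37.

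**4. How many of the 100 would be real?** True genes were given r = 0.3 by shifting Fisher z by atanh(0.3) × √72 = 2.63, and the true genes in the top 100 were counted.

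| Pool | 50 true | 100 true | 200 true |
|---|---|---|---|
| 40,000 | 16 | 31 | 54 |
| 2,000 | 35 | 62 | 89 |
| 308 | 46 | 82 | 99 |

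The range is 16 to 99 of 100, and the documents contain nothing that narrows it.

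**5. With error control on the gene-response step.** Under the complete null, Benjamini-Hochberg at 5% returned an empty list in about 95% of 4,000 runs at each pool size (mean about 0.06 genes). With 50 true genes at r = 0.3, it declared on average about 1, 7 and 20 genes for pools of 40,000, 2,000 and 308.

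**The case against.** The best defence is that this is a screen and the plan says so. D.2.e admits the multiple-comparison problem and speaks of possible candidates. D.1 hopes for consistent evidence in only a subset of the 100. A fixed list is a normal way to size a genotyping panel, and Aim 3 goes on to independent subjects. All of this stands, and it is why the point does not reach the later genetic conclusions. It does not supply an error rate for hypothesis 2, and it does not fit the statement "we will select 100 candidate genes that influence TZD response for Aim 2 study".

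Four stronger readings are tempting but not supported.

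- *Most of the 100 would be false.* This needs a small number of true genes and a large pool. D.2.f fits response models only to genes that pass the gate, and step 4 shows that the share of true genes could be low or very high.
- *Every listed gene would look strongly correlated.* This is true of 40,000 ungated genes. With a pool of 308, only about 15 would be nominally significant, and the reported adjusted R-squared values would show the weakness.
- *PCR is offered as confirming the correlation with response.* D.1 has it confirm expression differences, and nothing proposes re-correlating PCR values with response. The valid point is narrower: it cannot remove chance correlation in the same subjects.
- *The list fills with certainty.* It needs at least 100 genes to pass the gate, and judged function also enters. The pilot count of 308 makes this likely, though it came from two fat and three muscle pairs.

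**Conclusion.** The concern holds in limited form. No error control applies to the gene-response association, and the safeguards in the plan address other questions: drug effect on expression, measurement quality, and SNP association. Provided 100 genes pass the gate, the list would be filled under a complete null, with a 100th |r| anywhere from about 0.12 to 0.34 depending on pool size. The Aim 1c selection therefore cannot return a negative answer to hypothesis 2.

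These figures rest on independent genes, simple correlation, and pool sizes that the documents do not fix. How many of the 100 would be false cannot be determined. The defect is confined to hypothesis 2 and to the wording in Aim 2 and D.2.f that describes the genes as correlated with or influencing response. Using 100 genes as a genotyping panel is not at fault.

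**What to change.** Keep the panel of 100. In D.2.e (Specific Aim 1c) and the D.2.f statistical approach, add text to this effect:

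*Among the differentially expressed genes, the association between expression change and response will be tested by permuting response among subjects. Genes with an FDR of 5% or less will be reported as correlated with TZD response. Remaining places up to 100 will be filled by rank and labelled exploratory. The estimated FDR of the full list of 100 will be reported. Q-RT-PCR on the same RNA is technical validation of expression change only.*

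The gate should be settled without using the response data, so that restricting the permutation test to genes that pass remains valid. At the end of the D.2.f pathway text, describe the 100 genes as *selected for testing* instead of as influencing response, and align the Aim 2 description with this.

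The cost is computing and wording; laboratory work and genotyping are unchanged. The downside is real: fewer genes, possibly none, can be claimed as correlated with response. At r = 0.3 with 50 true genes the expected number declared is about 1 to 20, depending on the pool (step 5).

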experiments were conducted using Affymetrix U-133 Plus 2.0 chips to measure the expression of ~47,400 transcripts. Comparisons were made pre- versus post-rosiglitazone in the same subject, and changes in each gene were averaged. Fat tissue was analyzed separate from muscle tissue. At threshold p-values of $p < 0.05$ and 1.5 fold-change, we found 167 genes in subcutaneous fat and 141 genes in muscle that were significantly up- or down-regulated. Table 3 shows the 10 genes that had the largest changes in expression in fat (left) and muscle (right). In addition to our human data, the table shows the changes in same genes in mice fed a high-fat diet with or without rosiglitazone (5 mice/group, 30 mmol rosiglitazone/kg diet, 4 weeks). A comparison between the human genes responsive to rosiglitazone and their mouse HomoloGenes in Table 3 shows that the genes generally change in the same direction despite differences in magnitude. We acknowledge that with the small number of samples examined, these findings must be interpreted with great caution. Nevertheless, the comparison of genes responsive to rosiglitazone between humans and mice will disclose the genes that are co-regulated in the two species in a same manner. These genes are likely important for TZD-

mediated insulin sensitivity. These studies demonstrate that our group has the expertise and infrastructure to perform the proposed studies. They also show that these studies are likely to provide valuable information regarding genes and pathways that are associated with TZD response, which will be very useful in our choice and prioritization of candidate genes of importance to drug response.

Table 3. Five genes most up-regulated and five genes most down-regulated in fat and muscle tissue pre- versus post-rosiglitizone in humans. Mouse column shows expression changes in mice (see text). N/A, not on chip.

Fat			Muscle				
Gene Name	Fragment Name	Fold change		Gene Name	Fragment Name		
		Human	Mouse			Human	Mouse
Mitochondrial solute carrier protein	222529_at	20.39	3.8	ATPase, Class I, type 8B, member 1	241534_at	8.7	4.52
Leukocyte specific transcript 1	211582_x_at	9.84	N/A	Similar to protein sp:P39188	222375_at	5.31	N/A
T cell receptor beta chain BV20S1 BJ1-5 BC1	211796_s_at	8.09	3.09	FGF 18	206986_at	3.64	1.58
Amylase, alpha 2B; pancreatic, hypothetical protein FLJ25070	226999_at	7.27	N/A	SGT1, suppressor of G2 allele of SKP1 (S. cerevisiae)	244368_x_at	3.61	1.22

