to 2 is indicative of RNA. A ratio of 1.5 to 1.8 is considered good, while a ratio of 1.8 to 2.0 is considered excellent. We routinely achieve ratios above 1.9.

We further test the quality of the RNA using capillary electrophoresis in our Bioanalyzer (Agilent). This method is comparable to agarose gels, but much more sensitive, i.e. we can test as little as 5 nanograms of total RNA.

The labeling and hybridization is performed following Affymetrix standard protocols. For the following reverse transcription, transcription, labeling and hybridization steps, there are bacterial genes that are added to the sample to serve as controls and are examined as part of the low level dCHIP analyses. 15 micrograms of RNA is reverse transcribed using SuperScript and the other reagents from the One-cycle cDNA Synthesis Kit (Affymetrix). The next step is in vitro transcription and biotin labeling using the IVT Labeling Kit (Affymetrix). The sample is cleaned and hybridization controls are added. After hybridization, the microarrays are washed, stained with streptavidin phycoerythrin and scanned in our Affymetrix scanner. The quality of our hybridizations is very good; our normalization ratios range from 1 to 1.6.

Power considerations for the microarray studies. Although there is no consensus about which sample-size determination procedures for microarray comparison study are best, evidence indicates that a minimum of 5 biological cases per group for a two-group comparison study should be analyzed (4). Therefore, our current microarray comparison (before and after a 3-month rosiglitazone intervention) study with 75 subjects should have an adequate statistical power to detect most differentially expressed genes.

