Unsupervised clustering techniques will also be used to cluster the subjects according to the similarity of their gene expression profiles (before and after treatment), independently of clinical diagnosis or other investigator-designated categories. To limit noise and increase the strength of our findings, only genes with ample variability are used for cluster analysis (criterion values for variability will be determined empirically). The Hierarchical Ordered Partition and Collapsing Hybrid (HOPAH) (27) algorithm for building a hierarchical tree of clusters will be used for our cluster analysis. The number of clusters will be determined by Median Split Silhouette (MSS) (62) and biological consideration. The non-parametric bootstrap technique will be used for validating the HOPAH clusters. The clustering analyses will be assessed by using HOPAH package software in Bioconductor (27). Clustering of the

subjects based on gene expression would suggest a distinct, common underlying biological basis for disease in these subjects. Such an outcome could be a significant start in achieving one of our goals – a biology-based, rather than a clinical outcome-based classification of TZD response. Comparison of subject symptoms and clinical outcomes within- and across subject clusters based defined by gene expression profiling could be indicative of differences among subjects in response of TZD treatment.

Because the regulation of gene expression is a dynamic process, it is also important to identify and characterize changes in gene expression in response of TZD treatment among subject subgroups defined by expression profiling. Storey, et al. (73) proposed a general statistical method that identifies genes differentially expressed over time among different classes and have developed freely available software called EDGE. It is applicable to detecting differences in the behavior of expression in response to TZD treatment among different subgroups of the subjects. In addition to the pre-post comparison for each subgroup described above, the EDGE program will be used to identify genes that show significant differential expression in response to TZD treatment among different subjects.

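### The pre/post expression screen is paired by design, but its named rank tests are for independent groups and LIMMA is not stated to be paired

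*Combined protocol and SAP*

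**What the plan says.** The design is within-person. Section D.1 gives that as a strength: "Comparisons of gene expression profiles of the same tissue in the same person pre- and post- intervention should minimize many of the problems". The pilot arrays were handled that way (C.4.b): "Comparisons were made pre- versus post-rosiglitazone in the same subject, and changes in each gene were averaged". Section D.2.d sets a same-subject comparison for the repeated metabolic testing, which includes the biopsies.

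Only the Statistical approach paragraph of D.2.f assigns significance tests to the array contrast, and there the pairing disappears. The plan will "compare the expression profile of the muscle (and fat) tissues from pretreatment subjects to that from post-treatment subjects". Significance comes from LIMMA, with no subject block or paired contrast mentioned, or from "non-parametric methods (e.g., Kruskal-Wallis- or Mann-Whitney U-tests), using SAS software". Genes count as differentially expressed "only if they meet criterion values for fold-change and p-value (for example, >1.5 and <0.05, respectively"), and the criteria are varied until the calculated FDR is acceptable: "we anticipate using conservative FDRs in the range of 1-5"%.

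The power paragraph just before it relies on a two-group rule: "a minimum of 5 biological cases per group for a two-group comparison study should be analyzed". The screen's contrast is reused later in D.2.f for subgroups: "In addition to the pre-post comparison for each subgroup described above".

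**The concern.** Kruskal-Wallis and Mann-Whitney U treat the 75 pre and 75 post samples as 150 unrelated people. An unpaired LIMMA fit does the same. When a person's two samples are positively correlated, the unpaired test uses a standard error that is too large for the mean change. The p-values, and any FDR computed from them, are then too high.

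False positives do not increase. Genes can be lost, and in a discovery screen that is the error that matters. Because the plan tunes its criteria on the calculated FDR, an inflated value leads to tightening that is not needed. A gene that fails the screen is not scored in the regressions on clinical response that follow it.

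**Working it through.** The plan gives no numerical power for the array screen, only a statement that it is adequate, so there is no figure to reproduce.

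**Inputs from the documents:** 75 pairs; 40,000 genes (D.2.e, Specific Aim 1c); example gate of fold change above 1.5 and p below 0.05; FDR 1-5%.

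**Assumed, because the documents do not give them:** within-person correlation ρ of 0.3 / 0.5 / 0.7 (results in that order); SD of log2 expression; 5% of genes (2,000) changed, with true fold 1.75; two-sided tests; Benjamini-Hochberg adjustment; bivariate normal log2 values. One simulation run per cell.

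**Step 1: direction.** The unpaired standard error is SD × √(2/75); the correct one is SD × √(2(1−ρ)/75). The true size of the unpaired test at nominal 5% is therefore 2 × [1 − Φ(1.96/√(1−ρ))] = 1.9 / 0.56 / 0.03%. Simulated Mann-Whitney size is 2.1 / 0.8 / 0.05%; signed-rank holds 4.8-4.9%. At ρ = 0 the two approaches agree. At ρ = −0.3 the direction reverses (unpaired size about 9%).

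**Step 2: when the p-value matters at all.** An observed 1.5-fold change is log2(1.5) = 0.585. It just reaches an unpaired critical value z when SD = 0.585 / (z × √(2/75)) = 3.58/z:

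- p = 0.05 (z = 1.96): SD 1.83
- p = 0.001 (z = 3.29): SD 1.09
- p = 0.00001 (z = 4.42): SD 0.81

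Below these SDs the fold-change filter decides and the choice of test is irrelevant.

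**Step 3: example gate.** At SD 1.25, both tests pass 1,791 / 1,883 / 1,957 of the 2,000 changed genes. At SD 1.5, Mann-Whitney passes 1,726 / 1,802 / 1,911 and signed-rank 1,730 / 1,806 / 1,912. The loss is negligible.

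**Step 4: calculated FDR of that same list.** It is read here as the largest adjusted p-value in the list, which is a noisy measure.

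| SD | Mann-Whitney | Signed-rank | Actual |
|---|---|---|---|
| 0.8 | below 1% | below 1% | not shown |
| 1.0 | 6.8 / 10.3 / 6.9% | 1.3 / 0.9 / 0.0% | 0% |
| 1.25 | 50 / 64 / 36% | 19 / 1.8 / 0.3% | 1.8 / 0.05 / 0% |

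**Step 5: changed genes found with the 1.5-fold filter plus an FDR limit.**

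| Pairs | SD | FDR | Mann-Whitney | Signed-rank |
|---|---|---|---|---|
| 75 | up to 0.8 | 5% and 1% | identical | identical |
| 75 | 1.0 | 5% | within 0.2 points | within 0.2 points |
| 75 | 1.0 | 1% | 91 / 93 / 97% | 95 / 97 / 99.5% |
| 75 | 1.25 | 5% | 76 / 83 / 89% | 88 / 94 / 98% |
| 75 | 1.25 | 1% | 52 / 57 / 60% | 77 / 93 / 98% |
| 38 | 0.5 | 5% and 1% | no loss | no loss |
| 38 | 0.8 | 5% | 89 / 92 / 96% | 93 / 96 / 98% |
| 38 | 0.8 | 1% | 71 / 75 / 80% | 85 / 95 / 98% |

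The 38-pair rows are illustrative. That is the only subgroup size in the documents, and D.4.c gives it for the genetic analysis.

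**Step 6: LIMMA.** With ordinary t-tests as stand-in (SD 1.25, 1% FDR, 75 pairs), unpaired finds 59 / 64 / 70% and paired 81 / 94 / 98%.

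**Step 7: a mixed screen.** With 10% of genes at SD 1.5 and the rest at 0.5, the whole-screen result is 95.1 / 96.0 / 94.9% against 97.2 / 98.8 / 99.6% at 5% FDR, and 93.2 / 93.5 / 92.2% against 95.3 / 98.2 / 99.6% at 1%. Within the SD 1.5 genes at 1% it is 32 / 34 / 27% against 53 / 82 / 96%. With ρ of 0 or 0.1 the tests differ by at most 0.4 points overall.

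**Step 8: relaxed fold cut-off.** With a cut-off of 1.2, true fold 1.3, SD 0.5 and 1% FDR, the result is 84 / 89 / 93% against 93 / 98 / 99.7%.

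**The case against.** The best defence is that pairing is plainly intended. D.1, D.2.d and the pilot all describe same-subject comparison, and D.2.f specifies within-individual comparison for the adipose traits. LIMMA is named first and can be fitted paired; the rank tests are only examples. This stands to the extent that the plan does not commit to an unpaired analysis. It does not remove the conflict: an analyst who takes the non-parametric option as written would run a test that contradicts the design.

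Second, the harm depends on an SD and a correlation that the documents do not give, and it is nil at the example gate and at SD 0.8 or below with all 75 pairs. That is correct and limits the size of the point.

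Third, the calculated FDR could be read at list level instead: the expected number of unchanged genes passing both criteria, divided by list length. At SD 1.25 the unpaired standard error is 0.204, so 0.585/0.204 = 2.87, p = 0.0042, and 40,000 × 0.0042 ≈ 166; 166/1,883 is about 9%. At SD 1.0 the same calculation gives about 14 genes and 0.7%. On this reading the slight loss at SD 1.0 and 1% FDR disappears, but at SD 1.25 the unpaired figure still exceeds the 1-5% range. Adjusted p-values remain a fair reading of an FDR calculated with MULTTEST.

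Fourth, Specific Aim 1c correlates within-subject expression change with response over all genes, with no differential-expression gate. This second, paired route to the 100 candidates does limit the damage, and no calculation here shows that the final 100 would change.

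**Conclusion.** The concern holds and should be fixed. The plan names unsuitable rank tests for paired data and leaves the pairing of LIMMA unstated; it does not firmly choose an unpaired analysis. The problem is confined to the differential-expression screen and the subgroup pre-post comparisons. The regressions and correlations on per-subject change are already paired.

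If the screen is run unpaired, the error is conservative. Its size ranges from nothing to substantial: no practical loss at the example gate; 2-5 points of the whole screen at 5% FDR and 2-7 points at 1% in the mixed case of Step 7; and roughly 25 to 38 points at SD 1.25 and 1% FDR (77 − 52 = 25; 98 − 60 = 38). With fewer pairs, as in subgroups, the loss starts at a lower SD. All of this rests on positive within-person correlation, the premise of the plan's own same-person rationale, and on the assumed SDs.

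**What to change.** In the Statistical approach paragraph of D.2.f, for the pre-post contrast:

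- replace Kruskal-Wallis and Mann-Whitney U with the Wilcoxon signed-rank test on each subject's post-minus-pre log2 expression;
- state that LIMMA is fitted paired, with subject as a block or as an intercept model on within-subject differences, separately for muscle and fat;
- compute the FDR from those p-values;
- apply the same rule to the subgroup pre-post comparisons.

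This costs one sentence and no extra data. A subject missing one of the two biopsies drops out of the signed-rank test and of a difference-based model; LIMMA with subject as a random block can keep that subject.
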